10.1. Plasma Pharmacokinetics

10.1.1. Plasma Pharmacokinetics Concentration

Blood samples for PK analysis of total and unbound PB2452 concentration in plasma will be collected from all subjects at the following time points: before dosing (0 hour) and up to 28 days after initiation of the study drug (PB2452 or placebo) infusion. Since ticagrelor is not administered to cohort 1-3 subjects, only unbound PB2452 concentration data will be collected for cohort 1-3 subjects. Specific collection times for each cohort relative to the initiation of the study drug (PB2452 or placebo) infusion on Day 1 are listed in the table below:

Summary of Pharmacokinetic Assessments for PB2452	
Cohorts 1-6	-10 minutes, 0.5, 1, 1.5, 2, 3, 4, 6, 8, 12, 24, 48, and 72 hours, and 7 and 28 days
Cohorts 7-8	-10 minutes 5 minutes and 0.25, 0.5, 1, 2, 3, 4, 6, 8, 8.25, 8.5, 9, 10, 11, 12, 16, 20, 24, 32, and 48 hours, and 7 and 28 days
Cohorts 9-10	-10 minutes, 5 minutes, 0.25, 0.5, 1, 2, 3, 4, 6, 8, 10, 12, 14, 16, 20, 24, 28, 32, 36, 48 hours, 7 and 28 days

Plasma samples for determining total and unbound concentrations of ticagrelor and its active metabolite AR-C124910XX, will be collected from subjects in Cohorts 4 through 10 at the following timepoints: before dosing (within 10 minutes prior to the initiation of the study drug infusion [Hour 0]), and up to 48 hours following the initiation of study drug infusion on Day 1. Of note, subjects in Cohorts 4-6 will be administered the 5th ticagrelor dose and study drug infusion simultaneously, whereas subjects in Cohorts 7-10 will be administered the 5th ticagrelor dose two hours before the study drug infusion initiation on Day 1.

Specific collection times for each cohort relative to the initiation of the study drug (PB2452 or placebo) infusion are listed in the table below:

Summary of Pharmacokinetic Assessments for Ticagrelor and Active Metabolite AR-C124910XX	
Cohorts 4-6	-10 minutes and 0.5, 1, 2, 3, 6, 12, 24 and 48 hours
Cohorts 7-8	-10 minutes, 5 minutes and 0.25, 0.5, 1, 2, 3, 6, 8, 10, 12, 14, 16, 20, 24, 32 and 48 hours
Cohorts 9-10	-10 minutes, 5 minutes, 0.25, 0.5, 1, 2, 3, 6, 8, 12, 14, 16, 20, 24, 28, 36 and 48 hours

Concentrations that are below the limit of quantification (BLQ) will be treated as zero for descriptive statistics. Mean BLQ concentrations will be presented as BLQ, and the SD and coefficient of variation (CV) will be reported as not applicable. Missing concentrations will be excluded from the calculations.

For each analyte, plasma concentration data will be listed by subject and summarized by time point for each dose level using descriptive statistics (number of subjects, mean, SD, CV, median, minimum, and maximum). Plasma concentration versus time profiles for each subject will be presented graphically. The mean plasma concentrations versus scheduled time profiles by dose will be presented graphically.

Scatter plots of total and unbound plasma ticagrelor and AR-C124910XX versus total and unbound PB2452 plasma concentration will be prepared for all cohorts, as appropriate.

10.1.2. Plasma Pharmacokinetic Parameters

The PK parameters of PB2452, ticagrelor, and AR-C124910XX will be determined using noncompartmental methods using Phoenix WinNonlin Version 6.4 or higher or SAS® Version 9.3 or higher. For PK analysis, BLQ values will be treated as zero with the exception that a BLQ value between 2 quantifiable concentrations will be set as missing. If consecutive BLQ concentrations are followed by quantifiable concentrations in the terminal phase, those concentrations after BLQ concentrations will be treated as missing. Missing concentrations will be treated as missing from the PK parameter calculations.

The following PK parameters, if data permits, will be calculated for total and unbound plasma PB2452 using actual sampling times.

PB2452 PK parameters:

Parameter	Description
C_{\max}	Observed maximum plasma concentration
T_{\max}	Time to reach the observed maximum plasma concentration

AUC _{0-t}	Area under the plasma concentration versus time curve (AUC) from time 0 to the time of last quantifiable concentration (C _{last}); calculated using the linear-up/ log-down trapezoidal rule
AUC _{0-inf}	AUC from time 0 extrapolated to infinity, calculated as AUC _{0-t} + C _{last} /λ _z , where C _{last} is the last quantifiable plasma drug concentration and λ _z is the terminal phase rate constant.
AUC ₀₋₄₈	AUC from time 0 to 48 hours post-dose; calculated using the linear-up/ log-down trapezoidal rule
%AUC _{extrap}	Percentage of AUC _{0-inf} due to extrapolation from the time for the last quantifiable concentration to infinity, calculated as (AUC _{0-inf} - AUC _{0-t})/AUC _{0-inf} *100
λ _z	Terminal phase rate constant, determined by linear regression of the terminal points of the log-linear plasma concentration-time curve. The λ _z will not be estimated if the terminal phase of the log-concentration-time profile does not exhibit a linear decline phase, or if the regression coefficient (Rsq) is less than 0.8.
Rsq	Regression coefficient for calculation of λ _z
t _{1/2}	Terminal elimination half-life, calculated as t _{1/2} = ln(2)/ λ _z .
CL	Total body clearance, calculated as Dose/AUC _{0-inf}
V _d	Volume of distribution, calculated as CL/λ _z .

The following PK parameters, as appropriate and when data permit, will be calculated for ticagrelor and AR-C124910XX (total and unbound plasma) using actual sampling times:

Ticagrelor/ AR-C124910XX PK parameters:

Parameter	Description
C_{max}	Observed maximum plasma concentration
T_{max}	Time to reach the observed maximum plasma concentration
AUC_{0-t}	AUC from time 0 to the time of last quantifiable concentration (C_{last}); calculated using the linear-up/ log-down trapezoidal rule
AUC_{0-inf}	AUC from time 0 extrapolated to infinity, calculated as $AUC_{0-t} + C_{last}/\lambda_z$, where C_{last} is the last quantifiable plasma drug concentration and λ_z is the terminal phase rate constant.
AUC_{0-48}	AUC from time 0 to 48 hours post-dose; calculated using the linear-up/ log-down trapezoidal rule
%AUCextrap	Percentage of AUC_{0-inf} due to extrapolation from the time for the last quantifiable concentration to infinity, calculated as $(AUC_{0-inf} - AUC_{0-t})/AUC_{0-inf} * 100$
λ_z	Terminal phase rate constant, determined by linear regression of the terminal points of the log-linear plasma concentration-time curve. The λ_z will not be estimated if the terminal phase of the log-concentration-time profile does not exhibit a linear decline phase, or if the regression coefficient (Rsq) is less than 0.8.
Rsq	Regression coefficient for calculation of λ_z
$t_{1/2}$	Terminal elimination half-life, calculated as $t_{1/2} = \ln(2)/\lambda_z$.

Additional PK parameters may be calculated, as necessary. Pharmacokinetic parameters will be listed by subject and summarized for each dose level using descriptive statistics (number of subjects, mean, SD, CV, median, minimum, and maximum), with the exception of %AUCextrap, λz and Rsq, which will be listed only. Geometric means will be reported for AUCs and C_{max} .

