1.1.1 Non-clinical Pharmacology

Detailed descriptions of the non-clinical pharmacology of MEDI2452 (PB2452) may be found in the Investigator Brochure for MEDI2452 (PB2452). The key non-clinical pharmacology study findings for MEDI2452 (PB2452) are as follows:

- MEDI2452 (PB2452) binds ticagrelor and its active metabolite, AR-C124910XX, selectively and with a high affinity (equilibrium dissociation constant K_D 20 pmol/L).
- MEDI2452 (PB2452) rapidly neutralizes the unbound plasma fraction of ticagrelor and AR-C124910XX and thereby reverses ticagrelor- and AR-C124910XX-mediated inhibition of adenosine diphosphate (ADP)-induced platelet aggregation in a concentration- and dose-dependent manner in vitro (in human platelet-rich plasma) and in vivo (mouse and pig, dose-dependency data in mouse only).
- In mice dosed with ticagrelor to a supratherapeutic plasma exposure, MEDI2452 (PB2452) dosed before a tail cut reduced bleeding to a level that was not statistically different from that observed in mice not treated with ticagrelor.
- In pigs dosed to a supratherapeutic ticagrelor exposure on a background of ASA, MEDI2452 (PB2452) dosed after liver injury induced an elimination of free ticagrelor and AR-C124910XX in plasma within 5 minutes. The elimination translated into a gradual reversal of ticagrelor-mediated inhibition of ADP-induced platelet aggregation and numerical, but nonsignificant, improvements in mean arterial pressure, blood loss, and survival.

Non-clinical pharmacology studies have demonstrated that MEDI2452 (PB2452) binds with high affinity and selectivity to the P2Y₁₂ receptor antagonist ticagrelor and its active metabolite AR-C124910XX. MEDI2452 (PB2452) produces concentration (dose)-dependent reversal of ticagrelor- and AR-C124910XX-mediated inhibition of ADP-induced platelet aggregation. The activity in vitro and the rapid onset of effect observed in vivo translated to a

reduction of bleeding in ticagrelor-treated mice to a level that was not statistically different from that observed in mice not treated with ticagrelor.

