2.3. Exploratory

The exploratory objective is to evaluate the effect of MEDI2452 (PB2452) on the PK profile of unbound ticagrelor and unbound AR-C124910XX plasma concentrations.

3. Investigational Plan

This is a Phase 1, first-in-human, randomized, double-blind, placebo-controlled, single ascending dose, sequential group study to evaluate the safety, tolerability, PK, and PD of MEDI2452 (PB2452) with and without ticagrelor pretreatment when administered to healthy male and female subjects. All references to study drug within this statistical analysis plan (SAP) apply to MEDI2452 (PB2452) or matching placebo.

This study will have up to 10 cohorts and up to a total of 68 subjects with either 4 or 8 subjects in each cohort. The starting dose of MEDI2452 (PB2452) will be 100 mg and the planned doses for subsequent cohorts are 300, 1000, 3000, 9000, and 18000 mg. Other intermediate doses may also be tested but will not exceed 1800 mg.

The study will consist of a screening period (Days -45 to -4), check-in/pretreatment (Day -3 to Day -1), an in-house treatment period (Days 1 through 3 [Cohorts 1 through 8] or 4 [Cohorts 9 and 10]), and follow-up visits (Days 4, 7, and 28 [+2 days]). Subjects will receive an IV dose of study drug on Day 1.

On Day 1, subjects who meet all the inclusion criteria and none of the exclusion criteria will be randomly assigned to receive MEDI2452 (PB2452) or placebo in a ratio of 3:1 in all treatment cohorts as described below and as summarized in [Table 3-1](#).

Table 3-1 Summary of Treatment per Cohort

Cohort	Pre-MEDI2452 (PB2452) ticagrelor dosing to steady state (180 mg + 90 mg bid for 5 doses total)	MEDI2452 (PB2452) Dose (mg)	Number of subjects MEDI2452 (PB2452):placebo
1		100	3:1
2		300	3:1
3		1000	3:1
4	180 mg + 90 mg bid	1000	6:2
5	180 mg + 90 mg bid	3000	6:2
6	180 mg + 90 mg bid	9000	6:2
7	180 mg + 90 mg bid	18000	6:2
8	180 mg + 90 mg bid	18000	6:2
9	180 mg + 90 mg bid	18000	3:1 or 6:2*
10	180 mg + 90 mg bid	18000	3:1 or 6:2*

Abbreviations: bid, twice daily.

*Initially the cohort size will be 4 subjects (3:1); if needed for confirmation of PK/PD an additional 4 subjects (3:1) will be randomized in that same cohort.

Cohorts 1 to 3:

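### SAP 10.1.2 sets no time window for ticagrelor Cmax and Tmax, so in Cohorts 7-10 unbound Cmax could be the value drawn before PB2452 and show little or no effect

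*SAP*

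**What the plan says.** SAP 10.1.2 gives one parameter table for ticagrelor and its metabolite, covering total and unbound drug: these parameters, "as appropriate and when data permit, will be calculated for ticagrelor and AR-C124910XX (total and unbound plasma) using actual sampling times". Cmax is the "Observed maximum plasma concentration" and Tmax is the time to reach it. Neither has a start time, a window or a rule for a pre-infusion value. The AUCs run from time 0.

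SAP 10.1.1 schedules the first ticagrelor sample 10 minutes before the study drug infusion in all of Cohorts 4-10 and attaches Hour 0 to the start of that infusion. In Cohorts 4-6 the fifth ticagrelor dose is given together with the infusion, "whereas subjects in Cohorts 7-10 will be administered the 5th ticagrelor dose two hours before the study drug infusion initiation on Day 1". (This timing is the SAP's, which follows protocol amendment 5; the public protocol is dated 1 February 2018 and predates it.)

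The exploratory objective in SAP 2.3 is "to evaluate the effect of MEDI2452 (PB2452) on the PK profile of unbound ticagrelor and unbound AR-C124910XX plasma concentrations". Unbound parameters are summarised in Table 14.2.2.4, with geometric means for Cmax and the AUCs.

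SAP 11.2, by contrast, heads each PD parameter table as covering the time after the study drug infusion. The PK tables carry no such heading.

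**The concern.** At the -10 minute sample the subject has had four ticagrelor doses (Cohorts 4-6) or all five (Cohorts 7-10) and no PB2452. In Cohorts 7-10 the sample comes close to two hours after a dose, so it may lie near the peak. Protocol 1.1.1 describes rapid neutralisation of the unbound fraction, and reports that in pigs PB2452 "induced an elimination of free ticagrelor and AR-C124910XX in plasma within 5 minutes".

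If that carries over to humans, the largest unbound concentration in a PB2452 subject is the one drawn before PB2452. A Cmax taken over the whole profile then reports the untreated level as the level with PB2452, with Tmax at or before Hour 0. Table 14.2.2.4 could show nearly equal unbound Cmax for PB2452 and Placebo C7-C10 despite almost complete neutralisation. Cohorts 4-6 and 7-10 could also appear to disagree only because the timing of ticagrelor changed. No listed PK parameter measures the fall from the pre-infusion value or the lowest concentration reached.

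**Working it through.** The documents state no figure to reproduce. The check has two parts: timing, which the SAP fixes, and size, which needs assumed kinetics.

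**Timing (SAP 10.1.1)**
- Cohorts 7-10: 120 - 10 = 110 min, so the sample is 1 h 50 min after the fifth dose.
- Cohorts 4-6: 12 h - 10 min = 11 h 50 min after the fourth dose, which is a trough.

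**Model for untreated ticagrelor**
- From the SAP: doses 180, 90, 90, 90, 90 mg every 12 h (relative sizes 2, 1, 1, 1, 1), with the fifth at Hour 0 (Cohorts 4-6) or Hour -2 (Cohorts 7-10), and the SAP sampling grids.
- Assumed, not in the documents: one compartment, first-order absorption (ka), half-life 6-12 h.
- C(t) = sum over doses of a × ka/(ka - ke) × [exp(-ke·s) - exp(-ka·s)], where a is the relative dose, s the time since that dose, and ke = ln 2 / half-life.

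**Worked case: half-life 8 h, ka 1 per h, Cohorts 7-8 grid**
- ke = 0.693/8 = 0.0866, and ka/(ka - ke) = 1.095.
- Fifth dose at the -10 min sample (s = 1.833 h): 1.095 × (0.853 - 0.160) = 0.759.
- All five doses, first to fifth: 0.029 + 0.041 + 0.117 + 0.330 + 0.759 = 1.276.
- Untreated values after infusion start: 1.284 at 5 min, 1.285 at 15 min, 1.280 at 30 min, 1.257 at 1 h. The maximum is 1.285.
- Pre-infusion value over placebo post-infusion maximum: 1.276/1.285 = 0.99.
- Same case in Cohorts 4-6: 0.615 before infusion, maximum 1.283 at 2 h, ratio 0.48.

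**Ranges of that ratio (half-life 6-12 h)**

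| ka (per h) | Cohorts 7-10 | Cohorts 4-6 |
|---|---|---|
| 0.8-1.5 | 0.98-1.01 | 0.34-0.63 |
| 0.5-3 | 0.94-1.03 | 0.30-0.69 |

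With near-complete suppression after infusion start, Cmax in a PB2452 subject is the numerator. Where the ratio exceeds 1, the placebo Cmax is also the pre-infusion value under the literal rule, so the reported ratio is 1. The apparent fall in Cohorts 7-10 is therefore 0% to 1 - 0.94 = 6%.

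**Incomplete suppression.** A second set of assumptions used an untreated peak at 1-4 h, half-life 7 h, and 1-30% of unbound drug remaining for 12-24 h, followed by return to the untreated level (twice that level in one scenario). The ratio is unbound Cmax, PB2452 over placebo:

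| | Pre-infusion sample included | Post-infusion samples only |
|---|---|---|
| Cohorts 7-10 | 0.95-1.00 | 0.10-0.30 |
| Cohorts 4-6 | 0.35-0.52 | 0.10-0.30 |

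A true fall of 70-90% in Cohorts 7-10 would be reported as 0-5%.

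**What would undo this.** Unbound drug would have to return above its pre-infusion level. With half-life 6-12 h and ka 0.8-1.5 per h, that needs about 1.8-3.8 times the untreated level at 12 h, or 3.5-15 times at 24 h.

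**The case against.** The strongest reply is that the SAP nowhere says the pre-infusion sample enters Cmax. Hour 0 is the start of the infusion, actual sampling times are used, and a sample at -10 minutes is before time 0. The words "as appropriate and when data permit, will be calculated for ticagrelor and AR-C124910XX (total and unbound plasma) using actual sampling times" also leave an analyst room to drop it. This stands in part: inclusion is inferred from the absence of a window. But an AUC from time 0 needs a starting value, and this sample is the only measured one. For PB2452 itself, SAP 10.1.1 labels the pre-dose sample as 0 hour. Leaving the choice to the analyst means it can be made after the data are seen.

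The second reply is that the effect is not hidden. The objective concerns the unbound profile, not Cmax. Unbound concentrations are summarised by time point and plotted, unbound AUCs are reported, and further parameters are allowed. A Tmax at or before Hour 0 would itself reveal the artefact, and no test uses ticagrelor Cmax. All of this stands, and it limits the point to two parameters.

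Third, the kinetics are assumed, and the 5-minute figure comes from pigs at supratherapeutic exposure. Suppression need not be near complete in Cohort 4: the protocol's dose rationale gives 1000 mg as the lowest dose expected to be active, and there it coincides with a fresh ticagrelor dose. That stands too, so the Cohorts 4-6 ratios should not be applied to Cohort 4.

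**Conclusion.** The point holds as an unstated window whose literal reading misleads. Under the assumptions above, unbound ticagrelor Cmax in PB2452 subjects in Cohorts 7-10 would usually be the pre-infusion value, at 94-103% of the placebo post-infusion maximum, and would show little or no effect. In Cohorts 4-6 the effect would be blunted rather than lost where suppression is near complete, which is not established at 1000 mg.

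A reader might infer more, but the documents do not support it:
- That the study would miss the effect on unbound drug. The AUCs, time-point summaries and profiles would still show it.
- That Cmax is certain to show no effect. This depends on the analyst's reading, the time of the ticagrelor peak, and fast, sustained suppression in humans.
- That total ticagrelor is distorted in the same way. The argument rests on removal of unbound drug and does not carry over to total drug.
- That the percentages apply to AR-C124910XX. The model has no metabolite formation step, so they are shown for the parent only.

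**What to change.** In SAP 10.1.2, for Cohorts 4-10:
- Take Cmax and Tmax of ticagrelor and AR-C124910XX only from samples after the start of the study drug infusion. State infusion start as the time origin, and label the parameters accordingly.
- Keep the -10 minute value as the Hour 0 anchor for AUC, and report it separately.
- State how Cmax and Tmax are handled when every post-infusion unbound value is below quantification. The SAP sets such values to zero, and a geometric mean cannot include a zero.
- Optionally, for the unbound analytes, add the post-infusion minimum and the percent change from the subject's own pre-infusion value, shown beside the matching placebo group (C4-C6 or C7-C10).

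The cost is SAP wording and a few derived variables. All the samples are already scheduled.

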3.5.1 Pharmacokinetic Assessments

Plasma:

Blood samples for PK analysis of MEDI2452 (PB2452) in serum will be collected from all subjects at the following time points: before dosing (0 hour) and at 0.5, 1, 1.5, 2, 3, 4, 6, 8, 12, 24, 48, and 72 hours, and 7 and 28 days after initiation of the infusion.

Plasma samples for determining total concentrations of ticagrelor and its active metabolite AR-C124910XX, will be collected from subjects in Cohorts 4 through 9 at the following timepoints: before dosing (within 10 minutes prior to the initiation of the MEDI2452 [PB2452] infusion and 5th ticagrelor dose [Hour 0]), and at 0.5, 1, 2, 3, 6, 12, and 24 hours after the initiation of the MEDI2452 (PB2452) infusion and 5th ticagrelor dose. Additional samples will be collected from subjects in Cohorts 8 and 9 at the following timepoints: 0.5, 1, 2, 3, 6, 12, 24, and 48 hours after the Day 2 post-MEDI2452 (PB2452) 6th ticagrelor dose.

Plasma samples for determining unbound concentrations of ticagrelor and AR-C124910XX will be collected from subjects in Cohorts 4 through 9 at the following timepoints: before dosing (within 10 minutes prior to the initiation of MEDI2452 [PB2452] infusion and 5th ticagrelor dose [Hour 0]), and at 0.5, 1, 2, 3, 6, 12, and 24 hours after the initiation of the MEDI2452 (PB2452) infusion and 5th ticagrelor dose. Additional samples will be collected from subjects in Cohorts 8 and 9 at the following timepoints: 0.5, 1, 2, 3, 6, 12, and 24 hours after the Day 2 post-MEDI2452 (PB2452) 6th ticagrelor dose.

The following plasma PK parameters will be calculated for MEDI2452 (PB2452) using actual sampling times rather than scheduled sampling times:

- Area under the plasma concentration versus time curve (AUC) from time 0 to the time of last quantifiable concentration (AUC_{0-t})
- Observed maximum plasma concentration (C_{max})
- Time to reach the observed maximum plasma concentration (T_{max})
- AUC from time 0 extrapolated to infinity (AUC_{0-inf}) (if data permit)
- Terminal elimination half-life (t_{1/2}) (if data permit)
- Apparent clearance (CL) (if data permit)

The following plasma PK parameters will be calculated for ticagrelor and AR-C124910XX using actual sampling times rather than scheduled sampling times:

- C_{max}
- T_{max}
- AUC from time 0 to 12 hours after dosing (AUC₀₋₁₂)

- AUC from time 0 to 24 hours after dosing (AUC₀₋₂₄)
- AUC_{0-inf} (if data permit)
- t_{1/2} (if data permit)

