2.2. Secondary

The secondary objectives of the study are:

- To determine the PK of ascending doses of IV MEDI2452 (PB2452) in the presence and absence of ticagrelor
- To determine the PK of ticagrelor and its active metabolite AR-C124910XX in the presence and absence of MEDI2452 (PB2452)

- To assess the effectiveness of a single IV MEDI2452 (PB2452) dose in reversing ticagrelor antiplatelet activity by measuring P2Y₁₂ reaction units (PRU) with VerifyNow™ P2Y₁₂ assay and platelet reactivity index (PRI) with vasodilator stimulated phosphoprotein (VASP) phosphorylation assay by enzyme-linked immunosorbent assay (ELISA)
- To evaluate the PK and PD of restarting a single dose of oral ticagrelor 24 hours after MEDI2452 (PB2452) administration if a sixth dose of ticagrelor is given
- To evaluate the immunogenicity potential of MEDI2452 (PB2452)

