10.1.3. Plasma Pharmacokinetic Parameters Analysis

Dose proportionality will be tested using the power regression model for AUC_{0-inf} , AUC_{0-t} , and C_{max} of total and unbound PB2452 in Cohorts 4, 5, and 6.

A power model will be fit to describe the relationship between Y (C_{max} , AUC_{0-t} , and $AUC_{0-\infty}$) and X (dose) using the least-squares linear regression model [$\ln(Y) = \ln(\alpha) + \beta \ln(X)$, which is the logarithmic form of $Y = \alpha X^\beta$]. From each model, the intercept of regression line [$\ln(\alpha)$] and the slope of the regression line β will be presented along with the 90% confidence interval (CI) of the slope. This model will be fit for total and unbound PB2452 in Cohorts 4, 5, and 6. The dose proportionality will be declared when the 90% CI for β lies entirely within the critical region,

$$\left(1 + \frac{\ln(0.5)}{\ln(r)}, 1 + \frac{\ln(2.0)}{\ln(r)}\right)$$

where r is the ratio of the highest and the lowest dose included in the power model.

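### Two SAP objectives ask what PB2452 does to ticagrelor and AR-C124910XX exposure, but no PB2452-to-placebo ratio or interval is planned, and the only fixed AUC window is 0-48 h

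*SAP*

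**What the plan says.** Two objectives are comparative. SAP 2.2 includes "To determine the PK of ticagrelor and its active metabolite AR-C124910XX in the presence and absence of MEDI2452 (PB2452"). SAP 2.3 sets the exploratory objective "to evaluate the effect of MEDI2452 (PB2452) on the PK profile of unbound ticagrelor and unbound AR-C124910XX plasma concentrations".

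For total and unbound ticagrelor and AR-C124910XX, SAP 10.1.2 lists Cmax, Tmax, AUC0-t, AUC0-inf, AUC0-48 and terminal-phase quantities. AUC0-48 is defined as "AUC from time 0 to 48 hours post-dose; calculated using the linear-up/ log-down trapezoidal rule", and AUC0-t as "AUC from time 0 to the time of last quantifiable concentration". The analysis is: "Pharmacokinetic parameters will be listed by subject and summarized for each dose level using descriptive statistics", with geometric means added for AUCs and Cmax.

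The only PK inference is in SAP 10.1.3, which begins "Dose proportionality will be tested using the power regression model for" and covers PB2452 in Cohorts 4-6. The table list in SAP 15 agrees: the statistical-assessment tables are for PB2452 only, and the ticagrelor tables are summaries.

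The supplied protocol (3.5.1) also planned "AUC from time 0 to 12 hours after dosing" and the matching 0-24 h AUC for ticagrelor and metabolite. Neither is in the SAP, and SAP 12 mentions only QTc changes.

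**The concern.** Neutralising unbound ticagrelor is the mechanism behind the platelet result. The trial randomises a placebo group on the same ticagrelor pretreatment, so the effect of PB2452 on ticagrelor exposure can be estimated without bias. As planned, readers get adjacent columns of descriptive statistics and must form the ratio themselves, with no stated comparator and no interval.

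Two features make that harder:

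- **Window.** 48 h runs well past the end of every infusion, so hours with PB2452 present are averaged with hours when it may no longer act. AUC0-t is no substitute, because it stops at the last quantifiable value and that time can differ between arms.
- **Comparator.** SAP 4.1 first says placebo is pooled across cohorts for all presentations, then lists separate Placebo C4-C6 and Placebo C7-C10 groups. The choice matters: Hour 0 coincides with the 5th ticagrelor dose in Cohorts 4-6 but falls 2 h after it in Cohorts 7-10 (SAP 3 and 10.1.1).

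**Working it through.** **The plan's own figure.** SAP Table 3-1 gives three cohorts of 4 and seven of up to 8: 3×4 + 7×8 = 68, as stated in SAP 4.2. With Cohorts 9 and 10 left at 4 each, the total is 60. No power calculation exists to reproduce.

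**Subjects for a contrast (Table 3-1).** Placebo in Cohorts 4-6 is 3×2 = 6. Placebo in Cohorts 7-10 is 2+2+1+1 = 6, up to 4×2 = 8. Each PB2452 cohort has 6 subjects, or 3 in Cohort 9 or 10 if not expanded.

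**Infusion length against the window (SAP 7.3).** Cohorts 4-6: 0.5 h. Cohort 7: 5 min + 7 h 55 min = 8 h. Cohort 8: 15 min + 3 h + 8 h 45 min = 12 h. Cohorts 9-10: 15 min + 4 h + 12 h 5 min = 16 h 20 min. All fall well short of 48 h. Ticagrelor samples at 12 and 24 h are scheduled in every ticagrelor cohort (SAP 10.1.1), so AUC0-12 and AUC0-24 need no new sampling.

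**How much the window can dilute.** The documents give none of these inputs, so all are assumed: placebo declines mono-exponentially with half-life h of 6-12 h; unbound drug under PB2452 is a fraction f = 0.05 of placebo until time D and equal to placebo afterwards. With A(a,b) = 2^(-a/h) - 2^(-b/h), the AUC ratio over 0-W (W > D) is

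[f·A(0,D) + A(D,W)] / A(0,W).

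Example, h = 8, D = 12, W = 48: (0.05×0.646 + 0.338)/0.984 = 0.38.

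| Suppression lasts (D) | Ratio 0-12 h | Ratio 0-24 h | Ratio 0-48 h |
|---|---|---|---|
| 6 h | 0.37-0.44 | 0.49-0.63 | 0.52-0.70 |
| 12 h | 0.05 | 0.24-0.37 | 0.28-0.49 |
| 24 h | 0.05 | 0.05 | 0.11-0.24 |

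The mono-exponential profile is only a rough guide in Cohorts 4-6, where the 5th oral dose is given at Hour 0.

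**Precision of a ratio.** For n1 active and n2 placebo subjects, the 90% CI is the ratio times or divided by

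exp{ t(0.95, n1+n2-2) · √ln(1+CV²) · √(1/n1+1/n2) }.

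Between-subject CV is not in the documents; 30-60% is assumed. For 6 versus 6 at CV 30%: exp(1.812×0.294×0.577) = 1.36.

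| Active vs placebo | CV 30% | CV 40% | CV 60% |
|---|---|---|---|
| 6 vs 6 | 1.36 | 1.50 | 1.79 |
| 6 vs 8 | 1.33 | 1.45 | 1.71 |
| 3 vs 6 | 1.48 | 1.68 | 2.10 |

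Pooling variance over the four groups of 6 in Cohorts 4-6 (20 df, t = 1.725) narrows the 6 vs 6 factor only to 1.34-1.74.

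**Putting the two together (6 vs 6, D = 6 h).** At CV 60%, a 0-12 h ratio of 0.44 has an upper limit of 0.44×1.79 = 0.79, clear of 1. A 0-48 h ratio of 0.70 at CV 40% has limits 0.70/1.50 = 0.47 and 0.70×1.50 = 1.05, which include 1. With D = 12 h, even the 0-48 h ratio of 0.49 stays below 1 at CV 60% (0.49×1.79 = 0.88). The window therefore matters most if suppression is short.

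**BLQ rule (SAP 10.1.2).** BLQ counts as zero, except that a BLQ between two quantifiable values becomes missing, and quantifiable terminal-phase values after consecutive BLQs become missing. For unbound ticagrelor, quantifiable before infusion, BLQ during it and quantifiable again later is what an effective neutraliser would produce. The first exception then interpolates across the suppressed point and inflates the AUC. The second deletes the recovery and deflates it.

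**The case against.** The strongest reply is that this is a first-in-human study with no power basis, that neither objective is primary, and that the information is already reported. SAP 10.1.1 summarises every analyte by time point with individual and mean profiles. Unbound ticagrelor and metabolite have their own table, figures and scatter plots in SAP 15. The C4-C6 and C7-C10 placebo groups appear alongside the PB2452 cohorts, with geometric means, SD and CV. Much of this stands. A reader might infer that the plan hides early suppression or yields no information on its size; the documents do not support that. What these outputs lack is a pre-specified contrast. The allowance for additional PK parameters names none, so a window could be chosen after the data are seen. The SAP already gives a 90% CI for dose proportionality without a power basis, so an estimate here would not be out of place.

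Three other stronger readings also fail:

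- **Rebound cancels the effect in AUC0-48.** No document describes a rebound of unbound ticagrelor, and one large enough to do this would also distort AUC0-24.
- **Every planned AUC spans at least 48 h.** AUC0-t can end sooner.
- **The SAP wrongly dropped AUC0-12 and AUC0-24.** The supplied protocol is dated 01 Feb 2018, while the SAP follows amendment 5 of 03 August 2018, which was not supplied. The omission may be an amended decision. The gap against the SAP's own objectives remains either way.

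**Conclusion.** The point holds as a gap between objectives and analysis. Two objectives ask what PB2452 does to ticagrelor and metabolite PK, and the SAP plans no ratio, difference or interval, although a placebo group matched on ticagrelor timing exists. This rests on the text alone.

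The window is a secondary weakness, and its size rests on assumptions. With 6 h of suppression, the 0-48 h ratio is 0.52-0.70 against 0.37-0.44 over 0-12 h. With 12-24 h of suppression, the 0-48 h ratio is 0.11-0.49 and the effect would still show. Early neutralisation is documented only nonclinically and for the unbound fraction (Protocol 1.1.1); later recovery is an inference, and the documents do not say that total ticagrelor falls.

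**What to change.** Add to SAP 10.1.3, and as one table in SAP 15:

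- **Contrast.** Within each ticagrelor-timing block (Cohorts 4-6; Cohorts 7-10), report the geometric mean ratio of each PB2452 cohort to that block's pooled placebo with a 90% CI. Present it as estimation, not testing, and note that ratios within a block share a denominator.
- **Parameters.** Cmax, AUC0-12, AUC0-24 and AUC0-48, timed from the start of infusion, for total and unbound ticagrelor and AR-C124910XX.
- **Model.** One-way model on the log scale, with an unequal-variance or rank-based alternative named in advance for unbound values near the quantification limit.
- **BLQ handling.** State that the two set-to-missing exceptions in SAP 10.1.2 do not apply to the unbound ticagrelor and metabolite partial AUCs, because BLQ followed by recovery is the expected drug effect there. BLQ then stays at zero under the SAP's general rule, with linear interpolation where the log rule is undefined.
- **Comparator.** Reconcile the two statements on placebo pooling in SAP 4.1.

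The cost is SAP wording, some PK programming and one table, with no new samples. The downside is wide intervals: times or divided by 1.36-1.79 for 6 vs 6 at the assumed CVs, and up to 2.10 if Cohort 9 or 10 has only 3 active subjects.
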